## **5.2 Safety Endpoints/Variables**

### **5.2.1 Primary Safety Endpoint**

No primary safety endpoint has been defined.

[figure not shown]
### 5.2.2 Secondary Safety Endpoints

- Incidence of related treatment-emergent adverse events (TEAEs) in MP.
- Incidence of related TEAEs in OLEX period

[figure not shown]
For the definition of TEAEs, see [CCI](#)

CCI

CCI

## 6 Statistical Analysis Methods

Continuous endpoints (values and changes from baseline/ cycle baseline, where applicable) will be summarized by number of subjects in the respective analysis set/ population (N), number of values analyzed (n), mean, standard deviation, median, quartiles, minimum, and maximum. If relevant, the number of values imputed due to missingness (nimp) will be reported for efficacy variables (see [Section 6.4.1](#)). Mean, quartiles, and median will be reported to one decimal place more than the data were collected, for the standard deviation two decimal places more will be displayed; for derived data, an adequate number of decimal places will be chosen.

For qualitative endpoints, absolute and percent frequencies (n, %) and, if applicable, shift tables will be displayed. Frequency tables will include the number of missing values, if applicable. Percentages will be calculated using the denominator of all subjects in a specified population or treatment group. The denominator will be specified in a footnote to the tables for clarification if not otherwise obvious. Percentages will be reported to one decimal place. In frequency tables based on observed cases, number of missing values will not be presented and percentages will be based on number of observed cases (Nobs).

If not otherwise specified, statistical tests will be conducted two-sided at type I error rate 5%. P-values will be reported to four decimal places (e.g., p=0.0375). P-values below 0.0001 will be presented as '<0.0001'. Confidence intervals (CIs) will be two-sided 95%.

In general, values obtained at Visit 2 are defined as the baseline values. Where data is not recorded at Visit 2, the last measurement before start of treatment is defined as baseline value. These values will be analyzed as baseline (i.e. baseline flag is 'yes' for last record with non-missing value before first treatment in Study Data Tabulation Model [SDTM]). For cycle 2 values obtained at Visit 8 and for cycle 3 values obtained at Visit 13 will be used as cycle baselines.

### 6.1 Efficacy Endpoints and Efficacy Estimands

Primary and sensitivity analyses of primary efficacy endpoints (see [Section 6.1.1.1](#)) and confirmatory analyses of key secondary endpoints will be based on the target population of main primary and key secondary efficacy estimands (see [Section 5.1.1](#) and [Section 5.1.2](#), respectively). It is defined as "Male and female adults (18 years of age or older) with HFL, GFL, and LCL of moderate (score of 2) to severe (score of 3) intensity at maximum contraction as assessed by the investigator and the subject according to MAS, as randomized in this study: Subset of subjects randomized to UFL treatment group or to Placebo treatment group, grouped by randomized treatment assignment.". Further efficacy analyses will be based on the FAS if not otherwise specified. Statistical tests will be two-sided hypothesis tests for between treatment differences in general. Adequate descriptive statistics as specified at the beginning of [Section 6](#) above will be provided for all endpoints.

In case Visit 7/Visit 8 or Visit 12/Visit 13 is performed on same day MAS assessments from Visit 7/Visit 12 will be duplicated to be also analysed and listed at Visit 8/Visit 13.

### 6.1.1 Primary Efficacy Endpoints and Estimands

[figure not shown]
The primary endpoints will be proportions of GFL-, HFL- and LCL-responders as defined in [Section 5.1.1](#). These proportions will be compared for treatment groups U and P. It should be noted that Group L is not part of the primary efficacy analysis which has the objective to compare efficacy of simultaneous treatment of UFL with NT 201 versus placebo. Group L and Total NT 201 (Group U and Group L pooled) will be considered in the supplementary analyses of primary endpoints on the FAS, the PPS, observed cases in the FAS, observed cases in the PPS (see below), in supplementary analyses of key secondary endpoints, and in analyses of further secondary and other efficacy endpoints.

The three main primary efficacy estimands are defined in [Section 5.1.1](#) (see [CCI](#) for GFL, [CCI](#) for HFL, [CCI](#) for LCL).

#### 6.1.1.1 Primary analysis

The following main estimators for main primary estimands will serve as primary analysis: For comparison of proportion of GFL-, HFL- and LCL-responders in treatment groups U and P, Mantel-Haenszel stratum weights and the Sato variance estimator will be used to calculate the stratum-adjusted risk difference, with study site serving as stratum variable. For each anatomical region, the stratum-adjusted (common) difference in response rates between treatment Group U and Group P (reference) ("Group U" – "Group P") will be provided with two-sided p-value and 95% Mantel-Haenszel confidence interval (CI). The null hypothesis of the Mantel-Haenszel test is that the common difference in response rates is zero. The family-wise two-sided type I error level  $\alpha = 0.05$  will be controlled by a hierarchical test procedure based on two-sided tests with  $\alpha = 0.05$  as described in [Section 6.4.3](#).

CCI

Strategies for handling of ICES are described in [Section 6.4.6](#).

Missing data will be imputed so that all subjects in the target population of main primary estimands can be included in the analysis. CCI

[figure not shown]

CCI

Responder rates with two-sided 95% Wilson CIs will be provided as well for both treatment groups included in target population of main primary efficacy estimands, overall and per study site.

A similar SAS code to the following statements will be employed for this analysis (example for comparison of GFL responders):

 In the CSP, it was erroneously stated that the score from V3 (Day 8) is likely lower than the score to be expected at Day 30. This is no change to planned analyses since no change to the imputation rule is implied. Only the justification for imputing monotonously missing data at V4, V5, V6, and V7 with V3 data (conservative approach) was corrected.

CCI

[figure not shown]

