**Statistical analysis methods**

Adequate descriptive statistics will be provided for each efficacy endpoint and timepoint.

Primary and sensitivity analyses for primary efficacy endpoints will be based on the target population of main primary estimands which is defined as "Male and female adults (18 years of age or older) with HFL, GFL, and LCL of moderate (score of 2) to severe (score of 3) intensity at maximum contraction as assessed by the investigator and the subject according to MAS, as randomized in this study. Subset of subjects randomized to UFL treatment group or to Placebo treatment group, grouped by randomized treatment assignment." Further efficacy analyses will be based on the full analysis set (FAS) including all randomized subjects, if not otherwise specified.

The primary analysis of primary endpoints will be comparison of proportion of GFL-, HFL- and LCL-responders in treatment groups U and P by Mantel-Haenszel tests of the null hypothesis that the stratum-adjusted difference in response rates at Day 30 is zero, with study site serving as stratum variable.

The family-wise two-sided type I error level  $\alpha = 0.05$  will be controlled by a hierarchical test procedure based on two-sided tests with  $\alpha = 0.05$ . First, a test for superiority of U versus P will be conducted for proportion of GFL-responders, then for proportion of HFL-responders and finally for proportion of LCL-responders. The test procedure will stop once statistical significance could not be reached.

Group L will not be part of the primary efficacy analysis.

All safety analyses will be performed on the SES.

Listings and tables displaying incidences of related TEAEs in MP and OLEX will be provided by Medical Dictionary for Regulatory Activities (MedDRA) system organ class and preferred term by randomized study group and overall, for the total study period and by treatment cycle. For the analyses by treatment cycle, the denominator for the incidences will be adjusted to all subjects being treated in that treatment cycle.

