### **3 Determination of Sample Size**

Overall, 360 subjects are planned to be randomized to three treatment groups (UFL, LCL or Placebo) with a randomization of 2:1:1 at baseline visit V2.

The FDA required that the clinical development program includes at least 300 completed subjects who are treated simultaneously in all three anatomical areas (GFL, HFL, LCL) under placebo-controlled conditions to support safety. Since two pivotal studies are planned for demonstration of NT 201 efficacy and safety in the combined GFL, HFL and LCL treatment and assuming that up to 15% of the subjects will not complete the study, 180 subjects will be randomized per study to be treated in all three anatomical areas (Group U). A randomization ratio of 2:1:1 for the treatment groups in this study results in 90 subjects for each of the L and P Groups.

These sample sizes provide sufficient power also to assess efficacy under conservative assumptions. For proportions of 20% LCL-responders in Group U and 5% in Group P, a power of 93% is achieved for one-sided Fisher's exact test at  $\alpha = 2.5\%$ . Moreover, if proportions of HFL- and GFL-responders of at least 40% for Group U and at most 5% for Group P are assumed, the samples sizes provide power close to 100%.

In conclusion, when randomizing 180 subjects to Group U and 90 subjects each to Groups L and P, the study will have at least 90% power to establish efficacy of NT 201 using a hierarchical procedure for comparisons of proportions of GFL-, HFL-, and LCL-responders between Groups U and P. Assuming that about 15% of subjects will not complete the MP period, the proposed sample size will result in more than 150 completed subjects in Group U in this study. This number of completed patients in this study is considered sufficient to support the overall safety profile of NT 201 for simultaneous treatment of UFL.

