### 6.1.1.3 Subgroup Analyses

[figure not shown]
The primary analysis of primary endpoints will be conducted for two subgroups for the target population of main primary estimands. Subgroups are defined by BoNT pre-treatment status. Subjects will be distinguished on whether they have been treated with BoNT of any serotype prior to randomization at any time for any treatment indication or not (treatment naïve). Two-sided 95% Wilson CIs for proportions and 95% Mantel Haenszel CIs for stratum-adjusted differences in proportions with Mantel Haenszel test p-values will be provided for the three regions. ICEs will be handled as described in [Section 6.4.6](#).

The last three supplementary analyses described below in [Section 6.1.1.4](#) also constitute subgroup analyses. They will be performed for the three primary efficacy endpoints on subjects whose in-person attendance of the primary endpoint visit was not affected by COVID-19 pandemic. The target of estimation is specified in full detail in the definitions of three supplementary estimands [CCI](#). The population attribute is a subset of the population defined in [Section 6.1](#) for main primary estimands. For more details see [Section 6.1.1.4](#).

CCI

CCI

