#### 6.1.2.1 Key Secondary Efficacy Endpoints and Key Secondary Efficacy Estimands

Main estimators for key secondary estimands will be calculated for the target population of main key secondary estimands and ICEs will be handled as described in [Section 6.4.6](#).

Main estimators for main key secondary dichotomous MAS-based efficacy estimands ([Section 5.1.2](#)) correspond to main estimators for main primary estimands (see [Section 6.1.1.1](#)). Missing data will be imputed as described in [Section 6.1.1.1](#). For all three anatomical regions and for investigator's as well as subject's assessments on the MAS, stratum-adjusted differences in proportions for overall comparisons of treatment Group U versus Group P (reference) with corresponding 95% Mantel Haenszel CIs and Mantel-Haenszel p-values will be calculated. Responder rates with two-sided 95% Wilson CIs will be provided as well.

Main estimator for the main key secondary estimand based on subject's GAIS [cci](#) will be analysis of covariance with factors treatment group and site, and mean of baseline MAS for HFL, GFL, and LCL at maximum contraction assessed by subject as covariate.

cci

According to the definition of the key secondary estimand based on subject's GAIS [cci](#) specific ICEs will be handled by applying the composite strategy. In these cases, missing subject's GAIS ratings or ratings of [cci](#) (see [Section 6.4.6](#) on ICEs),

regardless of whether the GAIS score from subject assessment at Day 30 (V4) is available or whether it is missing for the respective subject.

Least squares (LS) means, standard error, and two-sided 95% CI per treatment group and LS mean treatment difference ("Group U" – "Group P") with associated two-sided 95% CI and t-Test p-value will be provided. The null hypothesis of this t-Test is that the LS mean treatment difference is zero.

[figure not shown]
CCI

The resulting value will be rounded to two decimals.

Multiplicity adjustment strategy for comparisons of treatment groups U and P on key secondary endpoints is described in [Section 6.4.3](#).

CCI

Results for Group L from any analyses will only be interpreted descriptively.

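### If the primary p-value uses the Sato variance, the only variance the readable text names, its two-sided size is about 6.1-6.3% at the planned 5% placebo rate, so the stated family-wise 0.05 is not held

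*SAP*

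**What the plan says.** SAP 6.1.1.1 and protocol 12.4.1.1 describe the primary analysis in the same terms: "Mantel-Haenszel stratum weights and the Sato variance estimator will be used to calculate the stratum-adjusted risk difference, with study site serving as stratum variable". In every region, the common difference between Groups U and P "will be provided with two-sided p-value and 95% Mantel-Haenszel confidence interval (CI"). The null hypothesis is a common difference of zero. The SAP introduces its code with "A similar SAS code to the following statements will be employed for this analysis", but the code itself is redacted.

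Elsewhere the test is named without a variance:
- Protocol synopsis: "Mantel-Haenszel tests of the null hypothesis that the stratum-adjusted difference in response rates at Day 30 is zero"
- SAP 6.1.1.3 (subgroups): "95% Mantel Haenszel CIs for stratum-adjusted differences in proportions with Mantel Haenszel test p-values will be provided for the three regions"
- SAP 6.1.2.1 (key secondaries): "with corresponding 95% Mantel Haenszel CIs and Mantel-Haenszel p-values will be calculated"

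Protocol 12.4.7.4 and SAP 6.4.3 state that the two-sided family-wise level of 0.05 is controlled by a fixed sequence: GFL, HFL and LCL responders, then the key secondary endpoints.

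The sample size (SAP 3, protocol 12.1) rests on a different test, taken at the 2.5% level: "For proportions of 20% LCL-responders in Group U and 5% in Group P, a power of 93% is achieved for one-sided Fisher's exact test". The condition set for the other two regions is "if proportions of HFL- and GFL-responders of at least 40% for Group U and at most 5% for Group P are assumed"; there, power is described as close to 100%.

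**The concern.** The natural reading of the visible text is a Wald-type test: the Mantel-Haenszel risk difference divided by its Sato standard error. That standard error is evaluated at the observed rates, not under the null. When response is rare and allocation is 2:1, a chance shortage of responders in the smaller placebo arm both widens the difference and shrinks the standard error. The test then rejects too often, mostly in favour of Group U.

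The level of each step matters because the sequence has no other protection:
- If all three primary nulls are true, the family-wise error is the size of the GFL test.
- If GFL and HFL work and LCL does not, it is approximately the size of the LCL test.

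LCL has the smallest planned effect and is the gate to every key secondary test.

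**Working it through.** **Inputs.** 180 in Group U and 90 in Group P (SAP 3). All randomised U and P subjects are analysed, with missing data imputed (SAP 6.1.1.1). Up to 12 sites (protocol 6.1), no pooling (SAP 6.4.5), randomisation stratified by site (protocol 8.2.1). Placebo rate 5% for LCL and at most 5% for GFL and HFL. Site sizes, block size and a normal critical value of 1.96 are my assumptions.

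**The plan's own figure.** Exact one-sided Fisher test at 2.5%, 180 versus 90, 20% versus 5%: power 93.5%, which reproduces the stated 93%. Its U>P size at 5% in both arms is 1.2%.

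**Formulas.** For site k let n1, n0 be the arm sizes, x1, x0 the responders, N = n1 + n0, m = x1 + x0 and w = n1·n0/N. Sums run over sites.
- d = Σ w(x1/n1 − x0/n0) / Σ w
- Sato variance = (d·ΣP + ΣQ)/(Σw)², where P = [n1²·x0 − n0²·x1 + n1·n0(n0 − n1)/2]/N² and Q = [x1(n0 − x0) + x0(n1 − x1)]/(2N)
- CMH (null) variance = Σ{n1·n0·m(N − m)/[N²(N − 1)]}/(Σw)², without continuity correction

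Reject if |d|/SE > 1.96. A non-positive Sato variance counts as no rejection. With one stratum the Sato variance equals the ordinary unpooled variance.

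**One table worked through.** 23/180 versus 5/90, single stratum, Σw = 16,200/270 = 60.
- d = 0.12778 − 0.05556 = 0.07222
- Sato: P = (162,000 − 186,300 − 729,000)/72,900 = −10.333; Q = (23·85 + 5·157)/540 = 5.074; variance = (−0.746 + 5.074)/3,600 = 0.001202; z = 0.07222/0.03467 = 2.08, significant
- CMH: m = 28; variance = [16,200·28·242/(72,900·269)]/3,600 = 0.001555; z = 0.07222/0.03943 = 1.83, not significant

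Smallest significant Group U count:

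| Placebo responders | Sato | CMH | One-sided Fisher |
|---|---|---|---|
| 4 | 20 | 22 | 23 |
| 5 | 23 | 25 | 26 |

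**Size under the null.** Each range spans exact enumeration of the single table and simulation of 12 equal sites:

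| Common rate | Sato two-sided | Sato U>P tail |
|---|---|---|
| 1% | 4.6-4.7% | 4.3-4.4% |
| 2% | 8.9-9.1% | 8.1-8.2% |
| 3% | 7.7-8.0% | 6.6-6.9% |
| 4% | 6.6-6.9% | 5.3-5.7% |
| 5% | 6.1-6.3% | 4.8-5.0% |
| 10-30% (assumed) | 5.3-5.5% | 3.0-3.8% |

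By enumeration the two-sided size exceeds 5% at every rate from about 1.1% to 5%. At 5%, layouts of 6, 8, 10 and 12 sites, equal or unequal, give 6.1-6.3%. Random site sizes with incomplete blocks of 4 or 8 give 6.0-6.2%. Site rates varying around a mean of 5% give 6.1%. CMH at 5% gives 4.6-4.8% two-sided and 1.8-1.9% in the U>P tail.

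**Family-wise error.** GFL and HFL at 40% versus 5%, LCL at 5% versus 5%, 200,000 trials: Sato 6.2% (U>P 4.9%), CMH 4.7% (U>P 1.9%).

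**Power.**

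| U versus P | Sato | CMH | One-sided Fisher |
|---|---|---|---|
| 20% vs 5% | 97.1% | 95.3% | 93.5% |
| 15% vs 5% (assumed) | 80.3% | 72.2% | 66.5% |

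Sato and CMH decisions differ in 1.8% of trials at 20% versus 5% and essentially never at 40% versus 5%.

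**The case against.** **The statistic may be defined in hidden text.** Besides the code, other blocks next to the primary analysis are redacted in both documents, and SAP 6.1.1.2 is not readable at all. The visible wording ties Sato to calculating the risk difference and then speaks of a Mantel-Haenszel test, which also fits a CMH p-value printed beside a Sato interval. This stands as a limit: the result is conditional. It does not make the CMH reading the more natural one, because the p-value and interval are attached to the Sato-based difference and no null variance appears in readable text.

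**The practical effect is small.** The two-sided excess at 5% is 1.1-1.3 points, and the cut-offs with 4 or 5 placebo responders differ by two Group U subjects, at Group U rates of about 11-14%, below the planned 20%. This also stands, and it limits the severity. The error claim, however, concerns the null and not the planned effects.

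**The figures at 2-3% come from extreme tables.** At 2%, 7.9 of the 8.2 points in the U>P tail come from tables with no placebo responder, where Sato rejects with 4 of 180 in Group U and CMH needs 8. At 3% it is 5.1 of 6.9 points. That is correct, but at the headline 5% rate such tables contribute only 1.0 of 5.0 points.

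**CMH is not balanced either.** Its U>P tail is 1.8-1.9% at 5% and 0.5% at 2%. Its opposite tail is 2.7-2.9% at 5%, 3.1-3.4% at 2%, and 4.2% at 1% in the single table. True, but its two-sided size is at most 5.3% in single-table enumeration over rates of 0.5-50% (4.6% at 5%, 3.8% at 2%), and its error in the direction of the efficacy claim stays below 2.5% at the planned placebo rates.

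**Conclusion.** The concern holds on the readable text. If the primary p-value is the Sato-based one, the two-sided size at the documents' 5% placebo rate is 6.1-6.3% and the U>P tail 4.8-5.0%, so the 0.05 family-wise control claimed for the three primary endpoints is not achieved there. On this reading the analysis test is also more liberal than the test used for sizing (U>P size 1.2%). The power statement is unaffected.

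The conclusion assumes a normal reference distribution and the planned 180:90 split. It is insensitive to the number and size of sites, but it depends on the placebo rate. For the MAS-based key secondaries the documents give no placebo rate; at assumed rates of 10-30% the size is close to nominal. If the hidden code uses a CMH p-value, the size problem disappears. This is worth correcting, but it does not threaten the trial.

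**What to change.** Before unblinding, state in SAP 6.1.1.1 and 6.4.3 and in protocol 12.4.1.1 and 12.4.7.4 that each MAS-based step is decided by the site-stratified CMH score-test p-value (null variance, two-sided 0.05). Keep the Mantel-Haenszel risk difference as the estimate. Replace the Sato interval with the stratified Miettinen-Nurminen score interval with Mantel-Haenszel weights. Its statistic at zero difference is algebraically the CMH statistic, so interval and test agree; simulated coverage is 95.3-95.8% at 5% versus 5% and 95.4-95.8% at 20% versus 5%.

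Keeping the Sato interval beside a CMH test is not advisable. Under the null at 5% the two would disagree in 4.4-4.7% of trials: in 2.9-3.2% the interval excludes zero without CMH significance, and in 1.5% the reverse occurs, in the placebo direction. At 2% they would disagree in about 10%. If the code already uses CMH, say so in the text and pair it with the score interval.

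The cost is an amendment to both documents and a procedure option. Power falls by 1.8 points at 20% versus 5% and by about 8 points at an assumed 15% versus 5%. The synopsis plans the last primary outcome visit for Q2 2021 and the SAP follows protocol version 4.0 of 24 June 2021, so on that timeline the change comes after Day 30 data collection. It must be documented as made before the unblinding that follows database close (protocol 11.3 and 12).

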### 6.1.1.3 Subgroup Analyses

[figure not shown]
The primary analysis of primary endpoints will be conducted for two subgroups for the target population of main primary estimands. Subgroups are defined by BoNT pre-treatment status. Subjects will be distinguished on whether they have been treated with BoNT of any serotype prior to randomization at any time for any treatment indication or not (treatment naïve). Two-sided 95% Wilson CIs for proportions and 95% Mantel Haenszel CIs for stratum-adjusted differences in proportions with Mantel Haenszel test p-values will be provided for the three regions. ICEs will be handled as described in [Section 6.4.6](#).

The last three supplementary analyses described below in [Section 6.1.1.4](#) also constitute subgroup analyses. They will be performed for the three primary efficacy endpoints on subjects whose in-person attendance of the primary endpoint visit was not affected by COVID-19 pandemic. The target of estimation is specified in full detail in the definitions of three supplementary estimands [CCI](#). The population attribute is a subset of the population defined in [Section 6.1](#) for main primary estimands. For more details see [Section 6.1.1.4](#).

CCI

CCI

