## 7 STUDY POPULATION

Subjects with HFL, GFL, and symmetrical LCL of moderate (score 2) to severe (score 3) intensity at maximum contraction as assessed by the investigator and the subject at study baseline visit according to the MAS will be enrolled in this study. The ratings of the investigator and the subject do not have to coincide as long as all ratings at maximum contraction are moderate or severe.

Eligible subjects are those who meet all of the inclusion criteria and who do not present any of the exclusion criteria prior to randomization to treatment groups. Subjects are to be recruited regardless of gender, ethnic background, and pre-treatment status. This study population will therefore be expected to be a representative sample of the target population for the indication of moderate to severe UFL.

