#### **8.2.1     *Methods of assigning subjects to treatment groups***

At baseline visit V2, subjects will be randomized 2:1:1 to one of the three treatment groups (Groups U, L, or P). Randomization will be done by using an IWRS. Randomization numbers and date of randomization will be recorded in the eCRF.

Randomization will be stratified by investigational site and will be in blocks of appropriate size. This will ensure an approximately equal ratio of treatment groups between sites. The block size will not be disclosed to investigators until the study is unblinded.

No other criteria for stratification of randomization will be applied.

If subjects are discontinued from the study during the MP, no replacement of subjects is planned.

In the MP, for each visit, the system will assign two medication boxes. The medication numbers are scrambled (they will not be in numerical order). Each site will receive scrambled medication numbers per delivery for the MP.

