#### **6.1.2.2 Further Secondary Endpoints**

Similar analysis strategy by region as described for supplementary analysis of primary endpoints on observed cases in FAS/ PPS (see [Section 6.1.1.4](#)) will be applied for the

further secondary dichotomous MAS-based efficacy endpoints defined for the MP. In particular, proportions of subjects with at least one-grade improvement in treatment groups U and P will be compared by stratum-adjusted and unadjusted differences in proportions with corresponding 95% Mantel Haenszel CIs and p-values. Moreover, 95% CIs for proportions and unadjusted difference in proportions will be provided.

[figure not shown]
Group L will only be considered for statistical analyses of MAS of the LCL region but not of the GFL and HFL regions. Analysis of stratum-adjusted and unadjusted differences in proportions will be performed separately for Group U vs. Group P, Group L vs. Group P, and Total NT 201 vs. Group P. For Group L, proportions with two-sided 95% Wilson CIs will be provided for all three regions, but difference in proportions compared to Group P only for LCL region. For LCL region, proportions will also be provided for Total NT 201.

GAIS as assessed by the investigator at Day 30 of the MP will be analyzed using analysis of covariance with factors treatment group and site, and mean of baseline MAS for HFL, GFL, and LCL at maximum contraction assessed by investigator as covariate (see [Section 6.1.2.1](#)). Comparisons will be made for Group U to Group P, Group L to Group P, and Total NT 201 to Group P. Two separate ANCOVAs, one for Group P, Group U and Group L and one for Group P and Total NT 201 (Group U and Group L pooled) will be conducted.

[figure not shown]
Results for all further secondary endpoints including any p-values and 95% CIs will only be interpreted descriptively. No type I error adjustment will be applied.

For further secondary endpoints only observed cases will be analyzed. Analyses will be provided for FAS and PPS.

[figure not shown]
CCI

CCI

CCI

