#### **6.4.5 Pooling of Sites**

No pooling of sites is planned.

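### SAP 6.1.1.3: in a small BoNT-history subgroup the site-stratified difference drops subjects and, near a 10% share, can lose its interval; an unadjusted difference with a Newcombe CI beside it is a cheap safeguard

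*SAP*

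**What the plan says.** SAP 6.1.1.3 states: "The primary analysis of primary endpoints will be conducted for two subgroups for the target population of main primary estimands". The subgroups are subjects with and without earlier BoNT treatment. The planned output for the three regions is "Two-sided 95% Wilson CIs for proportions and 95% Mantel Haenszel CIs for stratum-adjusted differences in proportions with Mantel Haenszel test p-values".

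The estimator comes from SAP 6.1.1.1: Mantel-Haenszel (MH) weights and Sato variance, "with study site serving as stratum variable". That section also plans responder rates "for both treatment groups included in target population of main primary efficacy estimands, overall and per study site"; 6.1.1.3 does not repeat the per-site part. The protocol synopsis foresees up to 12 sites, and SAP 6.4.5 says "No pooling of sites is planned".

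On BoNT history, Protocol 7 says "Subjects are to be recruited regardless of gender, ethnic background, and pre-treatment status". Randomisation is stratified by site, and Protocol 8.2.1 adds "No other criteria for stratification of randomization will be applied". Neither document gives an expected naive/pre-treated split.

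Elsewhere the sponsor reports both kinds of difference. Under SAP 6.1.2.2 the further secondary MAS endpoints "will be compared by stratum-adjusted and unadjusted differences in proportions with corresponding 95% Mantel Haenszel CIs and p-values".

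**The concern.** Blocking within site keeps U and P in proportion at each site for the whole trial, but not within a subgroup defined by BoNT history. If one subgroup is small, some sites will have only U or only P subjects in it. Those subjects drop out of the displayed difference while remaining in the Wilson rates printed beside it, so the two parts of the table describe different sets of subjects.

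Two consequences need separating. One is lost precision. The other is that the Sato interval can under-cover or shrink to zero width. The subgroup result is descriptive, so what is at stake is whether it can be read properly, not a confirmatory claim.

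**Working it through.** **Inputs.** SAP 3: 180 subjects in U, 90 in P; planning rates 20% against 5% (LCL) and 40% against 5% (GFL, HFL). Protocol synopsis: up to 12 sites. SAP 6.1.1.1: missing data are imputed, so all 270 U and P subjects are analysed. Assumed: the subgroup share f, 12 sites of 30 (15 U and on average 7.5 P each), and BoNT history mixed evenly across sites.

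**The plan's own figure.** Exact enumeration of one-sided Fisher's test at 2.5%, 180 against 90, 20% against 5%, gives 93.5% power. The stated 93% is reproduced.

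**Zero weight.** The weight of site s is nU·nP/(nU+nP), which is 0 if either arm is empty. The chance of an empty arm is about (1−f)^7.5 for P and (1−f)^15 for U.
- f = 20%: 0.8^7.5 = 0.188 and 0.8^15 = 0.035. Expected zero-weight subjects: 36 × 0.188 + 18 × 0.035 = 7.4 of 54, or 14%.
- f = 10%: 0.9^7.5 = 0.454 and 0.9^15 = 0.206. Expected: 18 × 0.454 + 9 × 0.206 = 10.0 of 27, or 37% (simulated mean 38%).
- f = 30%: 0.7^7.5 = 0.069 and 0.7^15 = 0.005. Expected: 54 × 0.069 + 27 × 0.005 = 3.9 of 81, or 5%.

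**Simulation.** 10,000 runs per setting, permuted blocks of 4 (2:1:1), 20% against 5%. Zero-width intervals count as misses.

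| Share f | U / P expected | At zero weight | MH variance / unadjusted | Sato coverage | Zero-width Sato CI | Newcombe coverage |
|---|---|---|---|---|---|---|
| 10% | 18 / 9 | 38% | 2.0 | 81% | 12.6% | 97% |
| 15% | 27 / 13.5 | 24% | 1.5 | 91% | 1.8% | 97% |
| 20% | 36 / 18 | 14% | 1.3 | 93% | 0.2% | 97% |
| 30% | 54 / 27 | 5% | 1.2 | 94% | 0% | 96% |
| 50% | 90 / 45 | 0.4% | 1.07 | 95% | 0% | 96% |

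The variance ratio is the squared ratio of the simulated SDs: (0.099/0.086)² = 1.3 at 20% and (0.175/0.124)² = 2.0 at 10%. The mean MH estimate was 0.149 to 0.151 against a true 0.15, so there is no bias. In the full population the variance ratio is 1.00 and Sato coverage 95%.

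**The 81% and the zero-width rate overlap.** A 40,000-run simulation at f = 10% gave no usable interval in 12.4% of runs and coverage of 92.5% where one existed: 0.925 × (1 − 0.124) = 0.81.

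**Why the width is zero.** With no responder at any site that has both arms, the MH difference is 0 and every term of the Sato variance vanishes, so the interval is [0, 0]. At f = 10% this occurred in 12.1% of runs; other zero-width cases made up 0.5%. Newcombe still works: for 0/18 against 0/9 the Wilson upper limits are 3.84/21.84 = 0.176 and 3.84/12.84 = 0.299, giving −0.30 to 0.18.

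**Sensitivity.**
- 40% against 5%, shares 10/15/20/30%: variance ratio 2.1/1.6/1.35/1.2; Sato coverage 87/92/93/94%.
- Uneven sites (5 to 60 subjects), 20% against 5%, same shares: zero weight 33/20/13/6%; ratio 1.9/1.4/1.3/1.2.
- 8 sites of 45, shares 10/20/30%: zero weight 25/6/1%; ratio 1.5/1.2/1.1.
- BoNT history clustered by site, f = 10%: zero weight 25% or 17%, depending on the degree of clustering, against 41% with even mixing in the same set of runs; ratio 1.6 or 1.4 against 2.1; Sato coverage stays near 82%.
- Large site differences (placebo rates of 0 or 30%, common difference 0.35), shares 10/20/30%: ratio 1.6/1.1/1.06.

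**The case against.** The strongest reply is that nothing in the documents shows a small subgroup. With an even split the effect is negligible, and stratifying by site matches the randomisation and keeps the subgroup estimates comparable with the primary result. This stands: the point is a contingency, and the planned estimator should stay.

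Second, a reader might infer that the SAP makes no provision at all. The documents do not support that. SAP 6.1.1.4 and the SAS code are blacked out, and 6.1.2.2 models its analysis, including unadjusted differences, on the supplementary analysis in 6.1.1.4. Unadjusted differences for the primary endpoints may therefore exist; whether they reach the BoNT subgroups cannot be seen.

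Third, much is derivable. The crude difference follows from the planned rates, Newcombe limits follow from the planned Wilson limits, and per-site rates, if carried into the subgroups, would show the empty arms. A [0, 0] interval would also be noticed. This stands too, but an interval worked out after the planned one has failed is a post hoc choice; a row fixed in advance is not.

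Fourth, Newcombe is not sharper at 20% against 5%. Mean full width is 0.39 against 0.37 for Sato at a 20% share, and 0.58 against 0.53 at 10%, where the Sato mean counts zero-width intervals as zero. At a 20% share its lower limit exceeds zero in 21% of runs against 42%. It is narrower only in places, for example 0.61 against 0.66 at 40% against 5% and a 10% share. It also ignores site.

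**Conclusion.** The point holds as a low-priority improvement, with medium confidence. On the readable text, the subgroup difference can rest on fewer subjects than the rates beside it. Under the stated assumptions, loss of precision is noticeable at a share of about 20% and marked at 10%. Interval failure is a separate matter: about 0.2% of runs at a 20% share, 1.8% at 15% and about 12% at 10%. It would be wrong to say that the Sato interval is likely to fail at 20%, or to read the 81% coverage at 10% as a second harm on top of the zero-width intervals.

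Because the two shares sum to 100%, at most one subgroup can be affected. The estimate is not biased, and the full-population primary analysis and the hierarchy in SAP 6.4.3 are unaffected. The size depends on an undocumented split, on the number of sites and on even mixing of BoNT history; fewer sites, clustered history or large site differences reduce the precision loss.

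**What to change.** In SAP 6.1.1.3, for both BoNT subgroups and all three regions, whatever the split turns out to be:

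- keep the site-stratified MH difference with its Sato CI and p-value;
- add one row with the unadjusted risk difference (U minus P) and its Newcombe 95% CI;
- add a footnote giving the number of U and P subjects at sites with an empty arm in that subgroup;
- state that both estimates are descriptive and always shown together, with neither chosen after seeing the data.

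If the blacked-out text already contains this, it is enough to confirm that it covers 6.1.1.3. The primary analysis and 6.4.5 need no change.

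The cost is one sentence, one table row and one footnote, and it extends what SAP 6.1.2.2 already does. The downsides are a second estimate that ignores site and an interval that is often somewhat wider, so it stands beside the MH result and does not replace it.
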